7.3 Enrollment (Day 0)

The Enrollment Visit can occur up to 45 days after the Screening Visit. All Enrollment procedures must occur on the same day.

Table 12: Enrollment Visit

able 12. E	able 12: Enrollment Visit Enrollment Visit – Visit 2				
	Component	Procedures			
		Review informed consent/ confirm participant's willingness to participate in study			
A	toother and Damilatana	Assess and confirm eligibility			
Adminis	strative and Regulatory	Review/update locator information			
		Provide reimbursement			
		Schedule next visit/contact*			
		Randomize to rectal tissue sampling schedule			
		HIV pre- and post-test counseling			
Dah	oviewel/Covenaclina	HIV/STI risk reduction counseling			
Ben	avioral/Counseling	Protocol counseling			
		Behavioral assessment			
		Review/update medical history			
		Perform physical examination			
		Perform male genital examination*			
		Perform pelvic examination*			
	Clinical	Perform rectal examination			
		Review/update concomitant medications			
		Treat or prescribe treatment for RTI/UTI, or STIs*			
		Disclose available test results			
	Pharyngeal	NAAT for GC/CT*			
	, ,	NAAT for GC/CT*			
	Urine	Urine dipstick/culture*			
		● Qualitative hCG ♀			
		CBC with differential and platelets*			
		Chemistries (AST/ALT/Creatinine)*			
ory	Blood	Syphilis serology*			
ooratory		HIV-1/2 test			
		Plasma for archive			
La	Pelvic	NAAT for GC/CT/TV* □			
		Anal swab for HPV			
		Rectal fluid for PD and biomarker			
	Anorectal	Rectal enema effluent for PD prior to biopsy collection			
		Rectal tissue for PD, histology, and archive			
		HSV 1/2 detection* NAAT for CO/CT*			
		NAAT for GC/CT*			
Stud	ly Product/Supplies	Offer condoms			

^{*} If indicated \(\rightarrow \)Female participants

7.4 Follow-up Visits

7.4.1 Dosing – Visits 3, 5, and 7

The first dosing on Visit 3 should occur approximately 14 days after the Enrollment Visit.

After a two-to-six-week washout period (to accommodate scheduling around the menstrual cycles of female participants) following each dosing visit, participants will return to the clinic for assessment. If no adverse events (AEs) that preclude continuation to the next dose are identified (based on product hold criteria in Section 9 and discretion of the loR/designee), participants will receive the next scheduled dose of the study gel. Please see the SSP Manual for additional information.

All participants will undergo PK and PD assessments within 24 hours after each gel administration. Participants will be randomized 1:1:1:1 to one of the following 4 time frames to provide samples of rectal tissue, rectal fluid, vaginal fluid (if applicable), and effluent from rectal lavage: 0.5-1 hour, 1.5-3 hours, 3.5-5 hours, and 24 hours following PC-1005 gel application. This time frame will remain consistent across gel volumes.. Procedures for the day of dosing are listed in

Table 13 below.

Table 13: Dosing Procedures

able 1	3: Dosing Procedures	ing Dunnadanan Maita O. F. and 7	
	Dosing Procedures – Visits 3 , 5, and 7 Component Procedures		
	Component		
Admi	inistrative and Regulatory	Noview aparte locater information	
		Provide reimbursement	
		Schedule next visit/contact	
Е	Behavioral/Counseling	Protocol counseling	
		Behavioral assessment	
		Review/update medical history	
		 Perform targeted physical examination* 	
		Perform male genital examination*	
		Perform pelvic examination*	
	Clinical	Perform rectal examination	
		Review/update concomitant medications	
		Treat or prescribe treatment for RTI/UTI, or STIs*	
		Disclose available test results	
		Record/update AEs	
	Pharyngeal	NAAT for GC/CT*	
		NAAT for GC/CT*	
	Urine	Urine dipstick/culture*	
		Qualitative hCG ♀	
		CBC with differential and platelets*	
حَ	Blood	Chemistries (Creatinine only)	
ato	2.000	Syphilis serology*	
Laboratory		Blood for PK ■ Blood fo	
La	Pelvic	Vaginal fluid for PK△♀	
		NAAT for GC/CT/TV*♀	
		Rectal enema effluent for PD prior to biopsy collection ∴	
	Anorectal	Rectal fluid for PK and PD	
	Allolottal	Rectal tissue for PK, PD, histology, and archive	
		HSV 1/2 detection*	
		NAAT for GC/CT*	
S	tudy Product/Supplies	Administration of study product	
		Offer condoms	

^{*} If indicated. ♀Female participants.

☆ Please reference the MTN-037 SSP Manual for additional details (www.mtnstopshiv.org)

▲ Participants will receive a single dose of study product (4 mL, 16 mL, or 32 mL) depending on dosing visit.

△= Participants will be randomized 1:1:1:1 to provide samples of rectal tissue, rectal fluid, vaginal fluid (if applicable), and effluent from rectal lavage in one of the following time periods after dose administration across gel volumes: 0.5-1 hour; 1.5-3 hours; 3.5-5 hours, or 24 hours. (Those assigned to the 24 hour time point to provide samples will do so at the 24-hr Post-dose visit instead of the Dosing visit).

♦ Blood will be collected pre-dose administration and at 1 hour, 2 hours, 3 hours, 4, hours, 5-6 hours and 24 hours after dose administration

NOTE: Participants will be instructed to call in to the clinic to report any issues related to the collection of samples via the flexible sigmoidoscopy. See SSP Manual for additional details.

7.4.2 24-Hour Post-Dosing Visits

Safety laboratory tests and blood for PK will be collected from all participants at the 24 hour post-dosing visit. Additionally, participants randomized to sample collection at 24 hours will have PK and PD samples collected.

Table 14: 24-Hour Post-Dosing Visits

usio 141 2	24-Hour Post-Dosing Visits - Visits 4, 6, and 8		
	Component	Procedures	
Administrative and Regulatory		 Review/update locator information Provide reimbursement Schedule next visit/contact π 	
Behavioral/Counseling		 HIV pre- and post-test counseling (Visit 8 only) HIV/STI risk reduction counseling (Visit 8 only) Protocol counseling IDI (Visit 8 only) 	
	Clinical	 Review/update medical history Perform targeted physical examination* Perform male genital examination* Perform pelvic examination* Perform rectal examination Review/update concomitant medications Treat or prescribe treatment for RTI/UTI, or STIs* Disclose available test results Record/update AEs 	
	Pharyngeal	NAAT for GC/CT*	
	Urine	 NAAT for GC/CT* Urine dipstick/culture* 	
Laboratory	Blood	 CBC with differential and platelets Chemistries (AST/ALT/Creatinine) Syphilis serology* HIV-1/2 test (Visit 8 only) Blood for PK◆π 	
	Pelvic	Vaginal fluid for PK△♀ NAAT for GC/CT/TV*♀	

	24-Hour Post-Dosing Visits - Visits 4, 6, and 8			
Component		Procedures		
		Anal swab for HPV		
		 Rectal enema effluent for PD prior to biopsy collection		
	Anorectal	Rectal fluid for PK and PD△π		
		 Rectal tissue for PK, PD, histology, and archive		
		HSV 1/2 detection*		
		NAAT for GC/CT*		

^{*} If indicated. ♀ Female participants.

NOTE: Participants will be instructed to call in to the clinic to report any issues related to the collection of samples via the flexible sigmoidoscopy. See SSP Manual for additional details.

7.4.3 48-Hour Post-Dosing Visits

Participants will be randomly assigned 1:1:1 to provide samples of blood, rectal tissue, rectal fluid, vaginal fluid (if applicable), and effluent from rectal lavage samples 48 hours following PC-1005 administration for one of the 3 gel volume levels (4 mL, 16 mL, or 32 mL). Participants will only attend one 48-hour visit during the study.

Table 15: 48-Hour Post-Dosing Visits

48-Hour Post-Dosing Visits - Visits 4a, 6a, and 8a			
	Component	Procedures	
Adminic	strative and Begulatory	Review/update locator information	
Adminis	strative and Regulatory	Provide reimbursement	
		Schedule next visit/contact	
Beh	avioral/Counseling	Protocol counseling	
		Review/update medical history	
		 Perform targeted physical examination* 	
		 Perform male genital examination* 	
		 Perform pelvic examination*	
	Clinical	Perform rectal examination	
		 Review/update concomitant medications 	
		 Treat or prescribe treatment for RTI/UTI, or STIs* 	
		Disclose available test results	
		Record/update AEs	
rat	Pharyngeal	NAAT for GC/CT*	
Laborat	Urine	Urine dipstick/culture*	
La		NAAT for GC/CT*	

π Please reference the MTN-037 SSP Manual for additional details (www.mtnstopshiv.org) regarding the appropriate procedures to complete for an Early Termination Visit.

^{△=} Participants will be randomized 1:1:1:1 to provide samples of rectal tissue, rectal fluid, vaginal fluid (if applicable), and effluent from rectal lavagein one of the following time periods after dose administration across gel volumes: 0.5-1 hour; 1.5-3 hours; 3.5-5 hours, or 24 hours. (Those assigned to the 24 hour time point to provide samples will do so at the 24-hr Post-dose visit instead of the Dosing visit).

^{♦=} Blood will be collected pre-dose administration and at 1 hour, 2 hours, 3 hours, 4, hours, 5-6 hours and 24 hours after dose administration

48-Hour Post-Dosing Visits - Visits 4a, 6a, and 8a		
Component	Procedures	
Blood	 Blood for PK Chemistries (AST/ALT/Creatinine)* CBC with differential and platelets* Syphilis serology* 	
Pelvic	Vaginal fluid for PK♀ NAAT for GC/CT/TV*♀	
Anorectal	 Rectal enema effluent for PD prior to biopsy collection ☆ Rectal fluid for PK and PD ☆ Rectal tissue for PK, PD, histology, and archive ☆ HSV 1/2 detection* NAAT for GC/CT* 	

^{*} If indicated. ♀Female participants.

NOTE: Participants will be instructed to call in to the clinic to report any issues related to the collection of samples via the flexible sigmoidoscopy. See SSP Manual for additional details.

7.4.4 Final Contact

The *Final Contact* (Visit 9) will occur either in-person or by phone approximately two to six weeks after the third dosing visit (32 mL) of PC-1005 gel application. This contact will also serve as the participant's study termination.

Table 16: Final Contact

Final Contact – Visit 9			
Component	Procedures		
Administrative and Regulatory	 Review/update locator information Provide reimbursement ~ Schedule next visit/contact* 		
Behavioral/Counseling	 HIV pre- and post-test counseling* HIV/STI risk reduction counseling* Protocol counseling* 		
Clinical	 Review/update medical history Perform targeted physical examination* Perform male genital examination* Perform pelvic examination* Perform rectal examination* Review/update concomitant medications Treat or prescribe treatment for RTI/UTI, or STIs* Disclose available test results Record/update AEs 		
্ৰ Pharyngeal	NAAT for GC/CT*		

Please reference the MTN-037 SSP Manual for additional details (www.mtnstopshiv.org)

	Final Contact – Visit 9		
	Component	Procedures	
		NAAT for GC/CT*	
	Urine	Urine dipstick/culture*	
		Qualitative hCG* ♀	
		CBC with differential and platelets*	
	Blood	Chemistries (AST/ALT/Creatinine)*	
	Biood	Syphilis serology*	
		HIV-1/2 test*	
Study Product/Supplies		Offer condoms*	

^{*} If indicated. ♀ Female participants. ~ Sites to reference SOPs regarding participant reimbursement.

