10.4 Sample Size and Power Calculations

Safety Endpoints

The proposed total sample size for assessing safety is approximately N=12 participants. This sample size is based upon the size of similar Phase 1 studies of microbicides for HIV prevention.

As a means to characterize the statistical properties of this study, Table 18 below presents the probability of observing zero, at least one, and two or more safety endpoints among the 12 participants for various "true" event rates:

Table 18: Analysis of Safety Event Frequency

Event Rate	P (0 events n=12)	P (> 1 event n=12)	P (> 2 events n=12)
1%	88.6	11.4	0.6
5%	54.0	46.0	11.8
10%	28.2	71.8	34.1
15%	14.2	85.8	55.7
25%	3.2	96.8	84.2
35%	0.6	99.4	95.8

An alternative way of describing the statistical properties of the study design is in terms of the 95% confidence interval for the true rate based on the observed data. Table 19 below shows the exact 2-sided 95% confidence intervals for the probability of an event based on a particular observed rate. If none of the 12 participants receiving a particular dose/volume of gel experience a safety event, the 95% exact 2-sided upper confidence bound for the true rate of such events for that dose/volume is 26.4%.

Table 19: Exact 2-sided 95% Confidence Intervals Based on Observing a Particular Rate of Safety Endpoints for Arms of Size 12

Observed event rate	Confidence interval (%)	
0/12	0.0, 26.4	
1/12	0.2, 38.4	
2/12	2.1, 48.4	

Additional participants may enroll in the study, at the discretion of the protocol team, to replace currently enrolled participants lost to follow-up or to permanent product discontinuation. Thus, in the event that additional participants are recruited for this purpose, the total sample size at the end of the study may slightly exceed 12 participants who received any dose/volume of PC-1005.

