#### **6.2 Treatment Exposure**

The number and percentage of participants administered each of the three (3) dose/volumes of gel at Visits 3, 5, and 7 will be displayed overall and by site. Participants will be classified into groups by dose/volume of gel based on the time from dosing up until just before the next higher dose/volume is administered (e.g., for the 4 mL dose/volume group, any safety endpoints which occur between the time of gel insertion at Visit 3 up until (but not including) the time the 16 mL dose/volume is administered at Visit 5.)

If applicable, the number and percentage of participants who had study product held during follow-up will be displayed overall and by site (along with the reasons why product was held).

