#### 8.1 Primary Safety Analyses

The primary safety endpoint is defined as follows:

Grade 2 or higher AEs as defined by the Division of AIDS Table for Grading the Severity of Adult and Pediatric Adverse Events, Corrected Version 2.1, July 2017, and/or Addenda 1, 2 and 3 (Female Genital [Dated November 2007], Male Genital [Dated November 2007] and Rectal [Clarification Dated May 2012] Grading Tables for Use in Microbicide Studies).

The number and the percentage of participants experiencing each safety endpoint will be tabulated by dose/volume of gel. This table will display a summary for any primary safety endpoint and for each individual safety endpoint. Each participant will contribute once in each category (i.e., only for highest severity AE for each participant) for the calculation of event rates for each dose/volume of gel. Exact binomial confidence intervals (Clopper-Pearson) will be calculated for each safety endpoint, even if no events occur for an endpoint for a particular dose/volume.

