#### 8.4 Other Safety Measures

Additional safety summaries include:

A listing of participants with abnormal findings on rectal examination after dose insertion (with dose/volume period when finding occurred) will be presented.

Concomitant medications are defined as any medication taken during the study. A participant listing of all concomitant medications will be presented.

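### By-volume safety reporting uses unequal windows: the 4 mL and 16 mL periods end with a required rectal exam and creatinine, the 32 mL period need not

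*Protocol*

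**What the plan says.** **Window.** SAP 6.2 groups safety endpoints by volume "based on the time from dosing up until just before the next higher dose/volume is administered". Its worked example closes the 4 mL window just before the 16 mL dose at Visit 5. No end is given for the 32 mL window, which has no later dose to close it. Protocol 8.3.1 collects AEs through the termination visit, and 7.4.4 makes Visit 9 that contact.

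**How the 4 mL and 16 mL windows close.** Under Protocol 7.4.1, after washout "participants will return to the clinic for assessment", and the next volume follows if nothing precludes it. Table 13 requires a rectal examination, creatinine, hCG (women) and AE recording at Visits 3, 5 and 7. CBC is done there only when indicated, and AST/ALT are not listed.

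**How the 32 mL window closes.** Visit 9 takes place "either in-person or by phone approximately two to six weeks after the third dosing visit (32 mL) of PC-1005 gel application"; Figure 2 labels it a phone call. Table 16 requires medical history, concomitant medications and AE recording. Rectal examination, CBC, chemistries and hCG are done only when indicated.

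**Reporting.** SAP 8.1: "The number and the percentage of participants experiencing each safety endpoint will be tabulated by dose/volume of gel", with exact confidence intervals. SAP 8.4: "A listing of participants with abnormal findings on rectal examination after dose insertion (with dose/volume period when finding occurred) will be presented". Neither section mentions that the windows end differently.

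**The concern.** A participant with an asymptomatic mucosal sign or a raised creatinine two to six weeks after 4 mL or 16 mL would have it found at the next dosing visit and, if found before dosing, assigned to the volume just given. The same finding after 32 mL need not be looked for. It would count if seen, because Protocol 8.3.1 includes unfavourable signs and abnormal laboratory results in the AE definition.

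The primary safety endpoint is reported by volume. Protocol 10.7.2 allows the volumes to be compared descriptively for tolerability and rules out formal comparison. Readers will therefore compare raw counts out of 12, and a difference in how hard one looks goes straight into those counts. The volume affected is the highest one, in the first study of this gel given rectally.

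**Working it through.** **1. The plan's own figures.** Protocol 10.4: "The proposed total sample size for assessing safety is approximately N=12 participants". With exact binomial formulas, P(0 events) = (1-p)^12. At p = 10% this is 28.2%, so P(at least 1) = 71.8%, as in Table 18; all of Table 18 reproduces. The 0/12 upper limit is 1 - 0.025^(1/12) = 26.47%, against the statement that "the 95% exact 2-sided upper confidence bound for the true rate of such events for that dose/volume is 26.4" per cent. These figures are sound, but they assume the same chance of detecting an event at each volume.

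**2. Order of exam and dose at Visits 5 and 7.** Table 13 lists the day's procedures without an order. Protocol 2.6 says each participant's safety assessments come before the next higher volume; 6.1 makes the next dose depend on finding no safety issue after washout; 7.4.1 puts the clinic assessment before the dose. Pre-dose is the natural reading, but none of these names the rectal examination or creatinine.

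**3. Required looks per volume, 12 completers, pre-dose reading.** Sources are Tables 13-16, and Protocol 7.8, 7.10 and 10.5 for sigmoidoscopy. Section 7.8 lists sigmoidoscopy as a possible part of the rectal examination. Three of the four sampling times fall on the dosing day, so 12 × 3/4 = 9 participants have one 0.5-5 hours after each dose. The other 3 have theirs at the 24-hour visit, already counted there.

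| Required post-dose look | 4 mL | 16 mL | 32 mL |
|---|---|---|---|
| Dosing-day sigmoidoscopy | 9 | 9 | 9 |
| 24-hour rectal exam | 12 | 12 | 12 |
| 48-hour rectal exam | 4 | 4 | 4 |
| End-of-window rectal exam | 12 | 12 | 0 |
| **Rectal total** | **37** | **37** | **25** |
| Creatinine, 24-hour visit + end of window | 12 + 12 = 24 | 24 | 12 |

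Rectal looks at 32 mL are 12/37 = 32% fewer. The whole difference lies in the last look.

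**4. Alternative order.** If the exam and blood draw follow dosing, the scheduled visit exams are 12 + 12 + 4 = 28 at every volume and creatinine is 24 at every volume. The asymmetry disappears.

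**5. Possible effect on counts.** Let p be the true Grade 2+ rate and f the share of affected participants detectable only by the end-of-window exam or creatinine. The documents do not give f; 0 to 50% is an assumed range. If that look is missing, the observable rate at 32 mL is q = p(1-f), and P(at least 1 seen) = 1 - (1-q)^12:

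| True rate | f = 0 | f = 10% | f = 25% | f = 50% |
|---|---|---|---|---|
| 10% | 71.8% | 67.8% | 60.8% | 46.0% |
| 15% | 85.8% | 82.5% | 76.1% | 60.8% |
| 25% | 96.8% | 95.3% | 91.7% | 79.9% |

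Example: p = 15%, f = 25% gives q = 0.1125 and 1 - 0.8875^12 = 76.1%.

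With a true 15% rate at both 16 mL and 32 mL, and the volumes treated as independent for illustration (the same participants receive both), the chance that the 32 mL count is the lower one is 38.4% at f = 0, 48.5% at f = 25% and 59.8% at f = 50%. The chance that it is the higher one falls from 38.4% to 27.7% and 17.2%.

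**The case against.** The strongest reply is that little is lost. The 24-hour visit is the same after every volume: rectal examination, CBC, AST/ALT/creatinine and AE recording. The 48-hour visits are balanced at four per volume. Visit 9 still requires AE recording, and a reported symptom can trigger an examination. Visit 8 adds an in-depth interview that the earlier 24-hour visits lack. These are single doses, comparisons are descriptive, and no test or dosing decision changes. All of this stands, and it limits the point to late, asymptomatic findings. It does not remove it: an examination prompted by symptoms cannot find what causes none.

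The unstated order at Visits 5 and 7 is also a fair objection. The pre-dose reading is well supported but not certain.

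A reader might infer more than the documents support:

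- *That 32 mL gets the weakest safety look overall, or appears safe by default.* Required assessments through 48 hours match at all volumes.
- *That required exams are 43% fewer at 32 mL (28, 28 and 16).* That count leaves out the nine dosing-day sigmoidoscopies per volume.
- *That a full laboratory panel is lost.* CBC and AST/ALT are not required at Visits 5 and 7 either, so creatinine is the only required safety chemistry that differs. The hCG test differs too, but SAP 8.3 reports it overall and by sex at birth, and neither document makes pregnancy a Grade 2+ endpoint.
- *That 7.4.1 contradicts the schedule, because "following each dosing visit, participants will return to the clinic for assessment".* Read in full, the passage concerns going on to the next volume, and none follows 32 mL.
- *That one could see, say, 3/12 at the lower volumes and 0/12 at 32 mL with no true difference.* That needs 25% of participants to have a late, persistent finding visible only on examination, and every Visit 9 to be by phone. Nothing in the documents supports such a rate.

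**Conclusion.** The point holds in limited form. On the pre-dose reading, the 4 mL and 16 mL windows end with a required rectal examination and creatinine, and the 32 mL window may end without either. Asymptomatic findings arising after 24-48 hours can then be recorded against the lower volumes and missed at 32 mL. This gap can only lower the 32 mL count relative to the others.

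Its size cannot be found from the documents. It depends on f, which may be close to zero after a single dose, and on how many Visit 9 contacts are by phone or done without an examination. The conclusion also rests on the order at Visits 5 and 7: if the items follow dosing, the difference largely vanishes. Tables 18 and 19 are not in error, and no formal inference is affected. What is affected is the descriptive reading across volumes, which can be protected with data already collected. The documents do not show that the visit schedule itself must change.

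**What to change.** All changes are to the SAP.

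1. **Sections 8.1 and 8.4.** Add the by-volume Grade 2+ AE table and the rectal-examination listing restricted to dosing through the 24-hour visit, where required assessments are the same at all three volumes. Base any descriptive statement across volumes on these.
2. **Full-window table.** Keep it, with a footnote that the 32 mL window has no required end-of-window rectal examination or creatinine. Report how many Visit 9 contacts were in person and by phone, and which assessments were done.
3. **Section 6.2.** State that the 32 mL window ends at Visit 9 or earlier termination. State that findings at Visits 5 and 7 are assigned by whether they were recorded before or after dosing.

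Cost: one extra table with its listing, a footnote and a few sentences, with no new data. The restricted table omits later events; these stay visible in the full-window table.
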